6.2.3 Dose reduction for decreased glomerular filtration rate (GFR)

Selinexor is not significantly eliminated by the kidney, therefore, no dose alteration of selinexor is required in patients with renal dysfunction.

However, creatinine increase and other renal effects have been observed in patients treated with selinexor. For their prevention, maintenance of adequate volume status is essential. Acute increases in creatinine are usually accompanied by disproportionately higher elevations of BUN. Therefore, all patients with renal dysfunction should be evaluated for volume status and fluid intake as well as electrolyte levels. Fluid repletion usually leads to resolution of creatinine increases in patients with dehydration associated with selinexor.

6.2.4 Missed or vomited doses

Missed Doses

Missed doses should be managed as follows:

If a dose was missed, the schedule of that week should be altered to accommodate two doses in that week with at least 36 hours between two consecutive doses.

If a dose must be skipped (e.g., due to recommendation of treating physician), the next dose will be taken as per schedule. Doses should not be administered less than 36 hours apart and all missed and delayed doses should be documented.

If a patient missed a full one- or two-week period of dosing for non-study treatment-related events (e.g., a required medical procedure or an unanticipated personal emergency), the days missed will be replaced. For example, if patient missed Cycle 2 Day 7 to Cycle 2 Day 14, then the patient will start the next dosing on Cycle 2 Day 7 following the break. Similarly, if a patient misses Cycle 3 Day 1 to Cycle 3 Day 15, then the patient will start the next dosing on Cycle 3 Day 1. In this fashion, laboratory and radiographic assessments remain appropriate for timing of the administration of anti-cancer therapy.

Vomited Doses

If a dose is vomited within 1 hour of ingestion, it will be replaced. If vomiting occurs more than 1 hour after dosing, it will be considered a complete dose.

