Diarrhea associated with selinexor is typically low grade and usually responds to treatment with standard anti-diarrheal agents (e.g., loperamide) and/or dose modification. Careful assessment of the patient's volume status is essential. Fluid replacement is important to prevent dehydration, fatigue and electrolyte abnormalities (e.g., hyponatremia).

Fatigue

Prevention of anorexia, vomiting, and dehydration may reduce fatigue. Hemoglobin levels must be optimized as anemia appears to contribute substantially to fatigue, particularly in patients with heavily pretreated hematologic malignancies. Please see the NCCN Guidelines for more information. In patients with adequate anti-tumor control on selinexor, once-weekly dosing is often associated with improvement in fatigue and other side effects.

Renal

Maintenance of adequate volume status is essential to prevent creatinine increases and other renal effects observed in patients treated with selinexor. Patients with acute increases in creatinine (usually accompanied by disproportionately higher elevations of BUN) should be evaluated for volume status and fluid intake as well as electrolyte levels. Fluid repletion usually leads to resolution of creatinine increases in patients with dehydration associated with selinexor.

Hematologic Effects

Thrombocytopenia

Selinexor may induce reductions in platelet counts, with minimal effects on numbers of megakaryocytes. The effects of selinexor on platelet generation are related to a slowing of maturation of megakaryocytes and a reduction in their average ploidy. There is no known effect on platelet function, and bleeding associated with low platelets has been uncommon.

Interruption or dose reduction of selinexor therapy, when appropriate, may lead to return of platelet counts in 1-3 weeks. See **Table 3** for specific guidance for managing Grades 1-4 thrombocytopenia.

Neutropenia

Standard granulocyte growth factors are highly effective for the treatment of neutropenia seen during treatment with selinexor and should be used early in patients whose neutrophil counts decline during

treatment. Patients should be instructed to report any symptoms or signs of infection such as fever, pain, sweating, and redness to their physician immediately.

Anemia

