Dose level -1	20 mg day 1 plus 40 mg day 2, 3 weeks on/1 week off
Dose level -2	40 mg once weekly, 3 weeks on/1 week off
Dose level -3	20 mg once weekly, 3 weeks on/1 week off
Dose level -4	Discontinue Dosing

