7.13 OVERDOSE

An overdose is a deliberate or accidental administration of any Karyopharm treatment to a study patient, at a dose greater than that which was assigned to that patient per the study protocol. If an overdose occurs, Karyopharm Pharmacovigilance should be notified immediately, and the patient should be observed closely for AEs. Resulting symptoms should be treated, as appropriate, and the incident of overdose and related AEs and/or treatment should be recorded. Overdose is to be reported on an SAE report form to Karyopharm pharmacovigilance regardless of whether or not an AE or SAE has occurred due to the overdose. If the overdose is associated with an SAE, the SAE report form must be submitted to Karyopharm pharmacovigilance within 24 hours of awareness. If there is no AE or SAE, the report must be submitted as soon as possible.

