9.8 Amendments to the Protocol

Any change or addition to the protocol can only be made in a written protocol amendment, and approved by the FDA where required, and the IRB. Only amendments that are required for patient safety may be implemented prior to IRB approval. Notwithstanding the need for approval of formal protocol amendments, the investigator is expected to take any immediate action required for the safety of any patient included in this study, even if this action represents a deviation from the protocol. In such cases, the PI should be notified of this action and the IRB at the study site should be informed according to local regulations but not later than 10 working days.

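### The missed-dose rule in section 6.2.4 fixes the week at two doses whatever the dose level, so read literally it doubles the weekly dose at the once-weekly levels -2 and -3

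*Combined protocol and SAP*

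**What the plan says.** Section 6.2.4 (Missed or vomited doses) tells the site that, if a dose was missed, the week's schedule "should be altered to accommodate two doses in that week with at least 36 hours between two consecutive doses". The sentence does not mention dose level, twice-weekly dosing or Table 2.

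Table 2, in section 6.2.1, sets four active dose levels. Level 0 is 40 mg twice weekly, three weeks on and one week off. The others are:

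- Level -1: "20 mg day 1 plus 40 mg day 2, 3 weeks on/1 week off"
- Level -2: "40 mg once weekly, 3 weeks on/1 week off"
- Level -3: "20 mg once weekly, 3 weeks on/1 week off"

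Two of the four levels therefore assign a single dose per week. The fatigue guidance in section 6.2.1 also mentions this schedule: for patients with adequate tumour control, "once-weekly dosing is often associated with improvement in fatigue and other side effects".

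The neighbouring rules deal with other situations. If a dose has to be skipped, for instance on the treating physician's advice, "the next dose will be taken as per schedule". Full one- or two-week gaps for reasons unrelated to study treatment are made up by resuming at the missed point. Vomited doses have their own one-hour rule. Doses missed during an infection are not replaced (section 6.2.2).

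**The concern.** The missed-dose rule names a fixed number of doses, while the number assigned per week depends on the dose level. At levels -2 and -3 the two disagree. A once-weekly patient who forgets the planned day and remembers within the same week falls under the unconditional sentence, which calls for two doses that week where one is assigned.

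The discrepancy falls only on patients who have already been reduced. Table 2 is a schedule of modifications for drug-related adverse events, and Table 3 steps the dose down one level at a time, so reaching level -2 from level 0 normally takes two reductions. Tolerability is a known problem here: section 1.1.5 reports that ten of the first 16 patients needed dose reduction or discontinuation for toxicity under the earlier 60 mg start, which is why the starting dose was lowered.

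Tablets are taken at home, and sites must instruct patients according to the protocol (sections 3.1.1 and 6.1.1). Instructions copied from section 6.2.4 would reach patients with nobody present to supply the intended limit. What is at stake is dosing safety, not the response-rate analysis.

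**Working it through.** **Inputs.** Assigned doses come from Table 2 (section 6.2.1). There are three dosing weeks per 28-day cycle (synopsis, treatment schema; section 3.1.1). The missed-dose rule comes from section 6.2.4.

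**The plan's own figure.** At the starting schedule, doses per cycle = 2 per week × 3 weeks = 6, which matches the 6 doses per cycle in the synopsis.

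**Formulas.**
- Assigned week = sum of the doses assigned in that week.
- Assigned cycle = 3 × assigned week.
- Affected week under the literal rule = two doses. At levels 0 and -1 these are the two assigned doses; at levels -2 and -3 they are twice the single dose.
- Cycle with one affected week = 2 × assigned week + affected week.

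| Level | Doses assigned per week | Assigned week (mg) | Affected week, literal rule (mg) | Ratio | Assigned cycle (mg) | Cycle with one affected week (mg) |
|---|---|---|---|---|---|---|
| 0 | 40 + 40 | 80 | 80 | 1.0 | 240 | 240 |
| -1 | 20 + 40 | 60 | 60 | 1.0 | 180 | 180 |
| -2 | 40 | 40 | 80 | 2.0 | 120 | 160 (+33%) |
| -3 | 20 | 20 | 40 | 2.0 | 60 | 80 (+33%) |

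At level -2 the affected week (80 mg) exceeds the level -1 week (60 mg) and equals the level 0 week. At level -3 the affected week (40 mg) equals the level -2 week.

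**More than one affected week in a cycle (upper bounds).** With k affected weeks:
- Level -2: 120 + 40k = 160, 200, 240 mg for k = 1, 2, 3, that is +33%, +67%, +100%. Three weeks would reach the level 0 cycle total.
- Level -3: 60 + 20k = 80, 100, 120 mg, with the same percentages.

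One affected week is the realistic case.

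**Does another rule close the gap?** No. The skip, full-week-gap, infection and vomited-dose rules each cover a different event. The 36-hour minimum controls spacing, not the number of doses in a week. None limits the two-dose instruction by dose level.

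**The case against.** The best defence is that the sentence was plainly written for twice-weekly dosing. The treatment schema and sections 3.1.1 and 6.1.1.2 all describe two doses a week, and a missed-dose rule is naturally read as restoring what was lost, not adding a dose that was never assigned. Table 2 says once weekly for the patients concerned, and dose modifications and missed doses must be documented. Many sites would infer the intent. That stands as a reason to expect the error rarely, but it leaves the instruction dependent on the reader overriding it.

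The exposed group is also likely to be small. Section 1.1.5 says most early patients ended up at 40 mg twice weekly, which is now level 0, and only ten further thymoma patients are planned (section 8.1.1). This is not a frequency for levels -2 and -3, but it points towards few cases.

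In the affected week, moreover, no single administration exceeds the assigned amount, doses are at least 36 hours apart against a half-life of about 6 to 8 hours, and 80 mg is the trial's own starting week. So the exposure is not untested. It is still the wrong one for a patient taken off that weekly dose for toxicity.

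Two supporting points are weak. Section 7.13 defines an overdose as drug given "at a dose greater than that which was assigned to that patient per the study protocol"; if section 6.2.4 itself prescribes the second dose, one can argue that it was assigned. The fatigue passage applies only to patients with adequate tumour control, and shows no more than that once-weekly dosing was foreseen. The conclusion needs neither.

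**Conclusion.** The concern holds: the rule is wrong as written for levels -2 and -3. Followed literally, it gives twice the assigned dose in the affected week (80 against 40 mg, and 40 against 20 mg) and 33% more over a cycle with one such week. Levels 0 and -1, physician-directed skips and infection holds are unaffected.

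This rests on four conditions: the patient is at a once-weekly level; the dose was missed and not skipped on advice or held for infection; enough of the week remains for two doses 36 hours apart; and the site or patient takes the sentence at its word. The documents give no frequency for any of these, so none is claimed. Sample size, power, type I error and the endpoint analyses are not touched. The correction should be made because the error would fall on patients already reduced, usually for toxicity.

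**What to change.** In section 6.2.4, replace the fixed count of two with a reference to the dose level. Suggested wording: *After a missed dose, rearrange the same week so that the patient receives the number of doses assigned at the current dose level in Table 2, and never more, keeping consecutive doses at least 36 hours apart.* The affected week then returns to 80, 60, 40 and 20 mg at levels 0, -1, -2 and -3, a ratio of 1.0 throughout. Any patient dosing instructions that repeat the current sentence should be changed to match.

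The cost is one phrase. Section 9.8 states: "Any change or addition to the protocol can only be made in a written protocol amendment", with IRB approval, and FDA approval where required. The change can travel with the next amendment. Dosing at levels 0 and -1 stays as it is.

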Study design	International, multicenter, open label phase II, Simons two stage design.
Anticipated start date	2018.01.01
Duration of study	24 month accrual and 6 months follow-up
Total number of sites	2 in the US
Study population	Adults with histologically confirmed, advanced, inoperable TETs who are progressing after treatment with at least one platinum containing chemotherapy regimen.
Objectives	
Primary objective	
 • To determine the efficacy of selinexor in adults with TETs determined by overall response rate (RECIST 1.1) in patients with advanced thymomas progressing after primary chemotherapy
Secondary objectives	
 • To determine the efficacy of Selinexor in adults with thymoma determined by overall response rate according to modified ITMIG response criteria • To determine six months PFS of patients with thymoma treated with selinexor • To determine overall survival of patients with thymoma treated with selinexor • To evaluate exploratory biomarkers for prediction of response to selinexor in patients with thymoma • To determine progression free survival in patients with advanced, inoperable thymoma treated with selinexor • To evaluate safety and tolerability of Selinexor
Planned sample size	
This study is comprised of 2 similar phase II trials, one running in US (25 patients) and one running in EU (25 patients):
 
Arm A: Thymoma
 
 • Stage 1: 15 patients • Stage 2: 10 patients (across all EU and US sites) 
Arm B: Thymic carcinoma (closed due to interim analysis)
 
 • Stage 1: 15 patients • Stage 2: 10 patients
Inclusion criteria	
 • Histologically confirmed advanced TET (thymoma) • Progression after Primary Chemotherapy

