Exclusion criteria	
 • No significant medical illness that in the investigator's opinion cannot be adequately controlled with appropriate therapy or would compromise the patient's ability to tolerate this therapy, including 
 - Unstable cardiovascular function - Known active hepatitis A, B, or C infection; or known to be positive for HCV RNA or HBsAg (HBV surface antigen) - Markedly decreased visual acuity - Active infection requiring intravenous antibiotics • Pregnancy or breast-feeding • Symptomatic brain metastasis requiring corticosteroids • Uncontrolled autoimmune disorders. Patients with autoimmune disorders under control on medication may be included. Patients with pure red cell aplasia may be included if haemoglobin levels are relatively stable on transfusions or medication • Significantly diseased or obstructed gastrointestinal tract, malabsorption, uncontrolled vomiting or diarrhea or inability to swallow oral medications • No dehydration of NCI-CTCAE grade ≥ 1 • Serious psychiatric or medical conditions that could interfere with treatment.

	
 • No history of organ allograft • No concurrent therapy with approved or investigational anticancer therapeutics
Treatment schema	Patients will receive oral Selinexor 40 mg twice weekly (Monday/Wednesday, Tuesday/ Thursday, or Wednesday/Friday). One cycle is 28 days. Patients will be dosed 3 weeks on and one week off in 4 week-cycles (6 doses/cycle). Treatment will continue until disease progression or the development of unacceptable toxicities or until deemed without benefit to the patient.
Primary parameter	
 • Overall response rate according to RECIST 1.1
Secondary parameters	
 • Overall response rate according to modified ITMIG response criteria • Six months PFS • Overall survival • Common Terminology Criteria for Adverse Events (CTCAEs) version 4.03
Exploratory parameters	
 • Exploratory biomarkers in archived tissue samples (TBD)
Study procedures	
 • CT scans after every 2 cycles of Selinexor • Physical examination every 2 weeks for the first 2 cycles, then every 4 weeks
Randomisation procedure	N/A

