¹ Prior to the first study-specific measures² Medical history includes baseline symptoms as well as a detailed history of prior cancer therapies including start and stop dates, disease progression during or after therapy, as well as discontinuations due to intolerance or any other serious illness.³ Applicable for women of childbearing potential. Serum β -HCG test within 7 days before the first dose of study drug. To be repeated by urine test, if date of first result exceeds the 7-day window⁴ Body height will be measured at screening only⁵ Vital signs: blood pressure, pulse and temperature⁶ Full physical examination for baseline and end of study visit. Physical examinations during the study should be symptom directed.⁷ Laboratory assessments do not need to be repeated on Day 1 if they were completed within the previous 7 days.⁸ Hematology: hemoglobin, hematocrit, mean corpuscular volume, white blood cell (WBC) count, WBC differential, neutrophils, platelets. WBC differential may be automated or manual as per institutional standards. Reticulocytes may be done only when clinically indicated. Hematology will be repeated twice a week in case of severe (grade 3-4) neutropenia or thrombocytopenia.⁹ Complete Serum Chemistry for baseline, cycles 1&2 and end of study/treatment visit include Sodium, Potassium, Creatinine, Glucose, Calcium ion, Magnesium, ALT, AST, Alkaline Phosphatase, Total Bilirubin, LDH, Albumin, TSH.¹⁰ Limited Chemistry including: Sodium, Potassium, Creatinine, Glucose, ALT, AST, Alkaline Phosphatase, Total Bilirubin¹² Disease status will be measured once every two cycles with CT scan of chest and abdomen.¹³ Tumour tissue will be obtained pre-dose provided that the patient has available archival biopsy tissue.¹⁴ Full ophthalmic examination is required at Screening, and, if clinically indicated, during the study. Prior to dilation, best corrected visual acuity, slit lamp examination including tonometry, following dilation; fundoscopy and slit lamp to document lens clarity – if a cataract/lens opacity is seen during the examination, the cataract/lens opacity will be graded according to a Grade 1-4 system.¹⁵ Nurse/research nurse can provide this in person or via phone call.¹⁶ Dispensing only occurs at Day 1 of Cycle 1 and 2.

1 Background and Rationale

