3.1 Study Design and Dosing Regimen

3.1.1 Definition of Treatment Cycle

One cycle is defined as 28 days. Selinexor 40 mg oral tablets will be administered twice weekly, either on Monday/Wednesday, Tuesday/Thursday, Wednesday/Friday, Thursday/Saturday, or Friday/Sunday in a 3-weeks-on and 1-week-off schedule. Patients will receive a supply of selinexor tablets for at-home dosing.

Study drug administration may be delayed for toxicity according to protocol Section 6.3.

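### On-treatment CT follows the cycle count, and section 6.2.4 moves it when a one- or two-week non-treatment gap is replaced, so the third scan can reach or pass six months and raise apparent six-month PFS

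*Combined protocol and SAP*

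**What the plan says.** The synopsis, under Study procedures, asks for "CT scans after every 2 cycles of Selinexor". Footnote 12 of the flow chart says "Disease status will be measured once every two cycles with CT scan of chest and abdomen". Section 3.1.1 states that "One cycle is defined as 28 days". None of these ties the scan to a calendar date counted from first dose. The flow chart allows 3 days either side of Day 1 from Cycle 3 onward.

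Section 6.2.4 sets a rule for longer gaps: "If a patient missed a full one- or two-week period of dosing for non-study treatment-related events", the missed days are replaced. In its second example, with Cycle 3 Day 1 to Day 15 missed, "then the patient will start the next dosing on Cycle 3 Day 1". It closes: "In this fashion, laboratory and radiographic assessments remain appropriate for timing of the administration of anti-cancer therapy". The scans therefore move with the reset cycle day.

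Other interruptions are treated differently:
- **Deliberately skipped dose (6.2.4):** "the next dose will be taken as per schedule", so nothing moves.
- **Infection (end of 6.2.2):** missed doses are not replaced.
- **Toxicity:** Table 3 says when to interrupt and restart, but not whether the cycle count stops. Section 3.1.1 refers toxicity delays to a section 6.3 that does not appear; the text runs from 6.2.8 to section 7.

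After treatment stops without progression, CT is calendar-based (3.1.4 and 5.2.4).

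The endpoint at issue is a secondary objective: "To determine six months PFS of patients with thymoma treated with selinexor". Section 8.2.4 specifies Kaplan-Meier with a median and 95% CI. It gives no rule for the date of progression, for late scans, or for a window around six months.

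**The concern.** Radiological progression can be recorded only when a scan is done. If the scan date moves with dosing, detection depends on exposure: a patient who misses two weeks is looked at two weeks later. Off treatment the same protocol uses the calendar, so two clocks feed one PFS curve.

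The effect is concentrated at six months because the third scan falls shortly before it. A patient whose tumour grew after scan 2, and whose scan 3 slips past the landmark, is counted as progression-free at six months. When progression is dated at the scan that shows it, the error is upward. There is no control arm in which the same error could cancel, and comparison with studies using fixed scan intervals becomes harder.

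**Working it through.** The plan states no target, precision or sample size for six-month PFS, so there is no figure of its own to reproduce. The check covers scan dates first, then the size of the effect.

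**Scan dates.** Inputs: two 28-day cycles per scan (synopsis, 3.1.1); replaced gaps of one or two weeks (6.2.4); window of 3 days either side (flow chart). Six months is taken as 365.25 / 2 = 182.6 days, an assumption because the plan gives no day count.

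Scan *k* is due at 56 × *k* days after first dose, plus any shift. Scans 1 to 3 fall at days 56, 112 and 168. The margin is 182.6 − 168 = 14.6 days.

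| Total shift before scan 3 | Scan 3 due (day) | With 3-day window | Against 182.6 |
|---|---|---|---|
| 0 | 168 | 165–171 | before |
| 7 | 175 | 172–178 | before |
| 14 | 182 | 179–185 | level; past only if at least 1 day late |
| 15 | 183 | 180–186 | past on the due date |
| 21 (7 + 14) | 189 | 186–192 | past throughout |

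The 15-day row applies if the Day 1 to Day 15 example is counted inclusively. The 21-day row needs one gap of each length; the plan sets no limit on repeated gaps.

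**Size of the effect.** Assume exponential PFS, S(t) = 2^(−t / median), with progression dated at the scan that shows it. Apparent six-month PFS is then:
- S(168) if scan 3 is on time;
- S(112) if scan 3 is late after a break that follows scan 2;
- S(126) if scan 3 is late and a 14-day break came before scan 2, moving scan 2 to 112 + 14 = day 126.

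The medians are assumptions, as the documents give none. For a 6-month median (182.6 days): S(168) = 2^(−168/182.6) = 52.9%, S(112) = 65.4%, S(126) = 62.0%.

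| Median PFS (months) | True S(182.6) | On time S(168) | Break after scan 2: S(112) | Rise (points) | Break before scan 2: S(126) | Rise (points) |
|---|---|---|---|---|---|---|
| 3 | 25.0% | 27.9% | 42.7% | 14.8 | 38.4% | 10.5 |
| 6 | 50.0% | 52.9% | 65.4% | 12.5 | 62.0% | 9.1 |
| 12 | 70.7% | 72.7% | 80.9% | 8.2 | 78.7% | 6.0 |
| 18 | 79.4% | 80.9% | 86.8% | 5.9 | 85.3% | 4.4 |

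Each rise is measured against the on-time reading and applies only to patients whose scan 3 is late.

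**Cohort effect** = share delayed × rise. Over the four medians, with the break after scan 2:
- 10% delayed: 0.1 × 5.9 = 0.6 to 0.1 × 14.8 = 1.5 points.
- 30% delayed: 0.3 × 5.9 = 1.8 to 0.3 × 14.8 = 4.4 points.

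**After a calendar anchor.** Scan 3 stays at day 168: days 165 to 171 with a 3-day window, 161 to 175 with a 7-day window. Both end before 182.6, so the delay effect is removed. The ordinary effect of assessing at intervals, S(168) − S(182.6), remains at about 1.5 to 3 points.

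**The case against.** The strongest objection is scope. A reader might infer that every dosing interruption moves the scans, and might point to section 1.1.5, where ten of the first 16 patients needed dose reduction or discontinuation for toxicity. The documents do not support this. The replacement rule covers only full one- or two-week gaps unrelated to study treatment. Skipped doses and infection gaps do not shift the schedule, and on toxicity the plan is silent. The ten of 16 are not counts of delays, and they predate the lower starting dose. Reducing a dose does not in itself move the cycle, and patients who stop without progression go onto calendar scans.

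A reader might also infer that a two-week gap by itself takes scan 3 past six months. It does not: day 182 is level with the landmark. A three-week delay needs more than one replaced gap, or some further slippage that the rule does not state. Nothing in the documents supports a large delayed share such as 40%.

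Two further points stand. The model treats every event as scan-detected, whereas deaths do not depend on scans and clinical progression ends treatment (3.1.2). If clinical progression counts as a PFS event, which is not stated, the effect shrinks. And with 25 thymoma patients, the 95% half-width around 50% is about 1.96 × √(0.25/25) = 0.196, or 20 points, well above the likely shift.

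These arguments limit size and reach. They do not remove the rule: 6.2.4 carries the scans along, and sampling noise does not offset an error in one direction. One misclassified patient in 25 moves the proportion by 1/25 = 4 points.

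**Conclusion.** The point holds within limits. The plan ties on-treatment CT to the cycle count and, for one defined kind of gap, expressly moves the scans with it. Scan 3 can then reach six months, and passes it if the visit is late within its window, the gap is 15 days, or a second gap occurs.

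The direction is upward when progression is dated at the scan. Among affected patients the rise is about 9 to 12.5 points at a 6-month median and about 4 to 8 points at 12 to 18 months. Over the cohort it is probably small: 0.6 to 1.5 points at 10% delayed, 1.8 to 4.4 points at 30%. This rests on exponential PFS, six months as 182.6 days, all events found by scan, and assumed medians and delayed shares. Median PFS is exposed to the same mechanism, but its shift was not quantified.

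A reader might infer that the trial's conclusion on activity is at risk. It is not: the stage 1 and final rules rest on response, and six-month PFS is secondary with no threshold. This is an inexpensive improvement of modest importance.

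**What to change.** 1. In the synopsis and footnote 12, replace the cycle-based schedule with: CT every 8 weeks (56 days) from first dose by calendar date, regardless of dose interruptions, delays or replaced days, with its own window (for example 7 days either side). This also settles scan timing during toxicity interruptions without altering any dosing rule.
2. In 6.2.4, delete the words *and radiographic* from the last sentence on missed doses.
3. Align the change with the parallel EU protocol. Section 8.1 pools the two trials, so amending only one would put two scan schedules in a single arm.
4. For patients already treated, add a six-month PFS sensitivity analysis that dates a progression found on a delayed scan at the originally scheduled scan date. This is deliberately conservative, since it assumes the progression would already have been visible.

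Cost: an amendment in both trials, with IRB approval and FDA approval where required (9.8), mainly for the 10 additional thymoma patients. Patients without gaps have the same number of scans. Some scans will no longer coincide with a Day 1 visit.
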